
The aim of this study is to demonstrate both a noninferior immune response with regards to geometric mean titer (GMT) ratio and seroconversion rate (SCR) difference for each strain and a superior immune response with regards to GMT ratio for at least 2 of the 4 strains of aQIV compared with a licensed nonadjuvanted quadrivalent influenza vaccine, 3 weeks after vaccination in adults 50-64 years of age. In addition, immunogenicity, antibody persistence, reactogenicity and safety will be assessed. Data from this study will be used to expand the licensure of the quadrivalent version of Fluad for the prevention of seasonal influenza in adults 50-64 years of age.
		

Disclosure Statement: This is a randomized immunogenicity study with 2 arms that is observer-blinded.
		

Study Objectives:
 
Primary Immunogenicity Objective(s):
 
1a. To demonstrate immunological noninferiority of aQIV versus a nonadjuvanted quadrivalent influenza vaccine comparator (QIV) in subjects 50-64 years of age, as measured by hemagglutination inhibition (HI)¹ geometric mean titers (GMTs) and seroconversion rates (SCRs) for each vaccine strain, at 3 weeks after vaccination.
		

¹ In case of lack of agglutination or agglutination mediated through neuraminidase for a specific strain using HI assay, immunogenicity for that strain will be assessed as measured by microneutralization (MN) assay as an acceptable alternative.

Success criteria:

Noninferiority will be demonstrated if the upper limit (UL) of the 95% confidence interval (CI) for the inter-group GMT ratio² (QIV/aQIV) is ≤ 1.5 for each vaccine strain, and the UL of the 95% CI for the difference in SCR³ (QIV-aQIV) is $\leq 10\%$ for each vaccine strain.

- 1b. To demonstrate that aQIV induces a superior immune response compared with QIV in subjects 50-64 years of age as measured by HI¹ GMTs at 3 weeks after vaccination for at least 2 of the 4 vaccine strains.

Success criteria:

Superior immune response will be demonstrated if the UL of the 95% CI for the inter-group GMT ratio (QIV/aQIV) is < 1.0 for at least 2 of the 4 vaccine strains.

Secondary Immunogenicity Objective:

- 2a. To demonstrate that aQIV induces a superior immune response compared with QIV in subjects 50-64 years of age as measured by HI¹ GMT for at least one vaccine strain at 3 weeks after vaccination.

Success criteria:

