A nonadjuvanted inactivated quadrivalent influenza vaccine administered as one 0.5 mL intramuscularly into the deltoid muscle. The vaccine is presented in a pre-filled needleless syringe (PFS). Each 0.5 mL dose contains 15 µg HA from each of the four influenza strains recommended by the World Health Organization for the 2021/2022 Northern Hemisphere influenza season for quadrivalent vaccines.		
Statistical Analyses:		
The primary analysis will be conducted on the immunogenicity data collected up to Day 22.		
Sample Size Estimation:		
With 1:1 randomization, a sample size of 1,816 evaluable subjects is chosen so that with one-sided alpha=0.025, there will be at least 90% power to achieve the primary objectives (1a and 1b). Assuming 10% drop out, the total sample size for the study is 2,018 subjects.		

Protocol Number: V118_23

Product Name: aQIV

Document Status: Final Version 3.0, Document Date: 11 Jul 2022

Name of Sponsor:	Protocol number:	Generic name of study vaccine(s):
Seqirus UK Limited	V118_23	MF59-adjuvanted Quadrivalent Subunit Inactivated Influenza Vaccine (aQIV) Licensed comparator: nonadjuvanted Quadrivalent Influenza Vaccine (QIV)

More details on the sample size calculation are provided in Section 8.5, Sample Size and Power Considerations of Primary Objectives.
 
aQIV will be tested against a licensed nonadjuvanted quadrivalent influenza vaccine (QIV). This study is powered to demonstrate the GMT superiority of aQIV vs QIV assessed by the four co-primary endpoints associated with primary objective 1b) at significance level of one-sided $\alpha=0.025$.
 
Hypothesis testing will be carried out by 1a) and 1b) sequentially. Only after the NI objectives are achieved, the superiority objectives will be tested. All tests are carried out with a one-sided alpha of 0.025 for each comparison. No adjustment for multiple endpoints for the primary objectives is necessary.
 
The Per Protocol Set (PPS) will be used for the noninferiority analyses, and the Full Analysis Set (FAS) will be used for superiority analyses.
 
Details on the statistical analysis can be found in Section 8, Statistical Considerations.
		

Interim Analysis: An interim analysis is not planned for this study.
		

Data Monitoring Committee: An independent Data Monitoring Committee will not be utilized for the study.
		

Schema

Table 0-1: Time and Events Schedule

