8.2.1.3 Success Criteria for Primary Immunogenicity Objective(s)

Success criterion for primary immunogenicity objective 1a is defined as:

Noninferiority of the aQIV immune response will be demonstrated if the UL of the 95% CI for the inter-group Day 22 GMT ratio (QIV/aQIV) is ≤ 1.5 for each vaccine strain, and the UL of the 95% CI for the difference in SCR (QIV - aQIV) is $\leq 10\%$ for each vaccine strain.

Success criterion for primary immunogenicity objective 1b is defined as:

Superiority of the aQIV immune response will be demonstrated if the UL of the 95% CI for the inter-group Day 22 GMT ratio (QIV/aQIV) is < 1.0 for at least 2 of the 4 vaccine strains.

The study is considered successful if primary objective 1a is achieved.

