No multiplicity adjustment to the CI levels will be implemented for the primary objectives. For the secondary endpoints, alpha was adjusted to 0.0127 for 1 out of 4 strain success for objective 2a and 2b so that the overall type I error is less than 0.05. The statistical hypotheses will be tested sequentially according to the order of the objectives. Details of the hypothesis testing procedure will be specified in the SAP.

Handling of missing values for immunogenicity data:

For immunogenicity data, it may be reasonable to consider missing immunogenicity values as missing completely at random (MCAR), i.e. not informative. Therefore, the immunogenicity analysis will comprise a complete case analysis only, without introducing any bias. Imputation methods will not be used.

Further details of the statistical methods will be provided in the SAP.

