Hypothesis testing will be carried out by 1a) and 1b) sequentially. Only after the noninferiority objectives are achieved, the superiority objectives will be tested. Only after the primary objectives are reached, secondary objective will be tested sequentially. All primary endpoint analyses will be carried out with a one-sided alpha of 0.025 for each comparison. No adjustment for multiple endpoints for the primary objectives is necessary.

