8.4 Multiple Comparisons and Multiplicity

Adjustment for multiple comparison and multiplicity is reflected in the CI of the success criteria, which kept the type I error under 5%. For secondary endpoint analyses, sequential testing and significance level adjustment will be applied to keep type I error under 5%.

For four out of four strain successes, with $\alpha=0.05$ for each strain, the overall type I error is $\alpha^4=0.00000625$.

For two out of four strain successes, with $\alpha=0.05$ for each strain, the overall type I error is $0.05^4+4 \times 0.05^3 \times 0.95+6 \times 0.05^2 \times 0.95^2=0.014019$.

For 1 out of four strain successes, with $\alpha=0.05$ for each strain, the overall type I error is $1-0.95^4=0.1855$.

Thus, for objective 1b): two out of four strain success, there is no need to adjust for $\alpha=0.05$ to keep the overall type I error under 0.05. But for objectives 2a) and 2b): 1 out of four strain success, α needs to be adjusted to 0.01274 so that the overall type I error = $1-(1-0.01274)^4=0.0499944$ which is less than 0.05. Therefore, the CI for the secondary objectives 2a and 2b have been adjusted to 98.73% to keep overall family wise error rate (FWER) under 0.05.

Confirmatory flow of tests and objectives, using a hierarchical testing approach

[figure not shown]
As soon as any success criterion is not met, confirmatory testing will stop.

PRIMARY OBJECTIVE 1a: Non-inferiority	
Tests using Antibody titer at Day 22: UL of 95% CI for GMT ratio (QIV/aQIV) for strain $i \leq 1.5$ and UL of 95% CI for SCR difference (QIV-aQIV) for strain $i \leq 10\%$, for all i , $i = 1$ to 4	Multiplicity consideration: not required, overall type I error is $< \alpha$, where $\alpha = 0.05$
	Analysis Set: PPS
Criterion: UL \leq threshold for all 8 CIs \Rightarrow Non-inferiority confirmed and continue testing	

PRIMARY OBJECTIVE 1b: Superiority for at least 2 strains - basic threshold	
Tests using Antibody titer at Day 22: UL of 95% CI for GMT ratio (QIV/aQIV) for strain $i < 1.0$, for at least 2 out of 4 strains	Multiplicity consideration: not required, overall type I error is $< \alpha$ Analysis Set: FAS
Criterion: CI UL $<$ threshold for at least 2 out of 4 strains \Rightarrow Superiority (basic threshold) confirmed and continue testing	

SECONDARY OBJECTIVE 2a: Superiority for at least 1 strain - higher threshold	

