According to the stepwise procedure the following superiority test(s) are only conducted if all above non-inferiority hypotheses can be rejected.

Superiority of aQIV to QIV (Objective 1b)

To demonstrate that aQIV induces a superior immune response compared to QIV in subjects 50-64 years of age as measured by HI GMTs at 3 weeks after vaccination for at least 2 of the 4 vaccine strains. aQIV will be considered to be superior to QIV if the following statistical criteria are met:

- The UL of the two-sided 95% CI for inter-group GMT ratio (QIV/aQIV) < 1.0 for at least 2 of the 4 vaccine strains.

The statistical hypotheses to be tested for the primary immunogenicity objective 1b correspond to:

$$H_{0k}: GMTr_k \geq 1, \text{ for at least 3 of the 4 vaccine strains at Day 22}$$

$$H_{ak}: GMTr_k < 1, \text{ for at least 2 of the 4 vaccine strains at Day 22}$$

where $GMTr_k$ ($k=1,2,3,4$) are defined as above.

Translating into \log_{10} transformed GMT titer values, the hypothesis for GMT ratios comparisons become

$H_{0k}: \mu_{QIV,k} - \mu_{aQIV,k} \geq 0$, for at least 3 out of 4 vaccine strains ($k=1,2,3,4$) at Day 22

$H_{ak}: \mu_{QIV,k} - \mu_{aQIV,k} < 0$, for at least 2 of the 4 vaccine strains at Day 22.

Statistical Models:

Let $\log_{10}(Y_{ijk})$ denote the \log_{10} -transformed HI titer Y_{ijk} . $\log_{10}(Y_{ijk})$ are identical, independent normal distributed random variables, where i denotes the vaccine group aQIV or QIV; $j=1,..,n$ denotes subject j , $k=1, 2, 3, 4$ denotes the four vaccine strains.

$\log_{10}(Y_{ijk}) \sim N(\mu_{ik}, \sigma_{ik}^2)$ with μ_{ik} , and σ_{ik}^2 unknown. μ_{ik} represents mean of the \log_{10} -transformed HI titer level in QIV, aQIV of strain k .

X_{ijk} , $i = \text{aQIV, QIV}$, $j=1,..,n$, $k=1, 2, 3, 4$ independent Bernoulli distributed random variables: $X_{ijk} \sim B(1, \pi_{ik})$, where π_{ik} represents the probability for seroconversion in aQIV, QIV for strain k .

Statistical tests for GMT ratios

HI antibody titers will be \log_{10} transformed and modeled using analysis of covariance with a qualitative factor for vaccine group (η_{ik} , $i = \text{aQIV, QIV}$), age stratum (α_{jk} , $j=1,2$), history of influenza vaccination within the 3 previous seasons (yes/no) (γ_{lk} , $l=1,2$), sex (ξ_{mk}), and a common slope (β) representing the impact of the \log_{10} - prevaccination antibody titer τ_{0ik} , for subject n ,

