11.4 Sequential Testing and Significance Levels

As described in section 8.4, the following test procedure will be used to keep the FWER at 2-sided 5% for primary and secondary hypotheses:

- Test hypothesis 1a) (noninferiority) and hypothesis 1b) (superiority) sequentially at 2-sided level of 5%.
- Only after the goal of hypothesis 1a) is achieved hypotheses 1b) will be tested at $\alpha=0.05$ level.

- Only after the primary goals 1a) and 1b) are achieved, the secondary hypotheses will be tested sequentially at $\alpha=0.05$ level.
- For secondary objectives, if both primary objectives are achieved, then 2a will be tested at alpha-0.01274 level (two-sided) for each strain.
- If hypothesis 2a is successful, then hypothesis 2b will be tested at alpha=0.01274 for each strain at Day 181.

The study is considered successful if the primary objective 1a (non-inferiority) is achieved.

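### The claim that objective 1b (superiority in at least 2 of 4 strains) needs no multiplicity adjustment rests on an error rate that applies only if all four strains are null; under the stated null hypothesis the one-sided error can reach 7.3%, against an intended 2.5%

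*SAP*

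**What the plan says.** Objective 1b follows 1a in a fixed sequence and is judged on unadjusted intervals. The protocol synopsis gives the criterion: "Superior immune response will be demonstrated if the UL of the 95% CI for the inter-group GMT ratio (QIV/aQIV) is" below 1.0 for at least 2 of the 4 strains. It also says: "All tests are carried out with a one-sided alpha of 0.025 for each comparison". Protocol 8.4.2.3.3 states: "No multiplicity adjustment to the CI levels will be implemented for the primary objectives". Protocol 8.5 adds: "No adjustment for multiple endpoints for the primary objectives is necessary".

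The justification is in SAP 8.4. With 0.05 per strain, the SAP computes 0.014019 as the type I error of two successes out of four and concludes: "Thus, for objective 1b): two out of four strain success, there is no need to adjust for" an alpha of 0.05. The same section finds that a one-of-four rule would have an error of 0.1855, and therefore widens the intervals for 2a and 2b to 98.73%.

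The null hypothesis for 1b, in SAP 11.2 and in Protocol 8.4.2.3.1, is a GMT ratio of 1 or more "for at least 3 of the 4 vaccine strains at Day 22". SAP 11.4 describes the whole scheme in these words: "the following test procedure will be used to keep the FWER at 2-sided 5% for primary and secondary hypotheses".

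**The concern.** The error rate and the hypothesis do not match. The 0.014 is the chance of two or more false positives when no strain is superior. The written null also contains the case of one truly superior strain and three with a GMT ratio of exactly 1. In that case the superior strain supplies one of the two successes, and a single false positive among the other three completes the claim. In effect 1b becomes a one-of-three rule on the null strains. SAP 8.4 itself recognises that a one-of-four rule needs adjustment, but neither document computes the error for this case.

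At stake is a primary superiority claim in a study meant to support wider licensure, and the truth of the FWER statement in SAP 11.4. Objective 1b also decides whether 2a and 2b are tested.

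**Working it through.** **Inputs.** Per-strain one-sided level 0.025 (upper limit of a two-sided 95% CI; Protocol synopsis and 8.5). 1,816 evaluable subjects, so 908 per arm. Log10 differences (SD) of 0.07 (0.46) for A/H1N1, 0.26 (0.61) for A/H3N2 and 0.14 (0.48) for B; SCRs from the same tables (Protocol 8.5, SAP 5). The documents give no correlation between strains, so the correlations below are assumptions.

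**1. The SAP's figure.** 0.05⁴ + 4 × 0.05³ × 0.95 + 6 × 0.05² × 0.95² = 0.01402. This reproduces 0.014019. It assumes four null strains, independence and a success probability of 0.05 each. At the one-sided 0.025 actually applied, the same sum gives 0.0036.

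**2. One strain superior, three at GMT ratio 1.** If the superior strain passes almost surely:

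- independence: 1 − (1 − 0.025)³ = 0.0731
- any dependence: at most 3 × 0.025 = 0.075
- if the superior strain is A/H1N1 at its planned 90% power: 0.9 × 0.0731 + 0.1 × P(at least 2 of 3 false positives) = 0.9 × 0.0731 + 0.1 × 0.0018 = 0.0660

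**3. Correlation.** Chance of at least one false positive among three equicorrelated normal statistics:

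| Assumed correlation | 95% CI | 98.33% CI |
|---|---|---|
| 0 | 0.0731 | 0.0248 |
| 0.3 | 0.0683 | 0.0238 |
| 0.5 | 0.0627 | 0.0223 |
| 0.7 | 0.0546 | 0.0196 |
| 0.9 | 0.0418 | 0.0149 |

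**4. Does passing 1a first protect 1b?** A strain with equal SCRs p in both arms passes SCR noninferiority with probability Φ(0.10/√(2p(1 − p)/908) − 1.96), which is 0.9988 at p = 0.76 and 0.9996 at p = 0.80. GMT noninferiority at a ratio of 1 passes with probability above 0.9999. A simulation of all eight 1a intervals followed by 1b used A/H3N2 at its planning values, the other strains equal between arms (SCR 76%, 80%, 80%), a normal approximation, SCR drawn independently of GMT, and 10 million draws per correlation. 1a passed 99.8% of the time. The 1b error was 0.0730, 0.0683, 0.0626 and 0.0545 at correlations 0, 0.3, 0.5 and 0.7, so there is almost no protection.

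**5. Level that restores control.** 0.025/3 = 0.00833 per strain, a two-sided 98.33% CI. With one superior strain the error is at most 3 × 0.00833 = 0.025 under any dependence. With none superior it is at most 4 × 0.00833/2 = 0.0167.

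**6. Power at 908 per arm**, Φ(δ/(σ√(2/908)) − z), with z = 1.960 or 2.394. For A/H1N1, 0.07/(0.46 × √(2/908)) = 3.242.

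| | 95% CI | 98.33% CI |
|---|---|---|
| A/H1N1 | 0.900 | 0.802 |
| A/H3N2 | ~1 | ~1 |
| each B strain | 0.99999 | 0.99993 |
| 1b, only A/H3N2 and A/H1N1 superior | 0.905 | 0.805 |

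The last row is 1 − (1 − 0.900) × 0.975² and 1 − (1 − 0.802) × 0.99167², under independence. If A/H3N2 and one B strain are superior, or all four are at planning values, power for 1b stays above 99.9% either way.

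**The case against.** The strongest reply is that the excess belongs to a narrow corner of the null. It needs one strain that passes almost surely and three at a GMT ratio of almost exactly 1. With the other three at 1.02 in independent tests (A/H3N2 superior, planning SDs), the error falls to 2.8%; at 1.05 it is 0.5%. The planning values have all four strains superior. The four titers come from the same sera, so positive correlation is plausible, and at 0.9 the error is 4.2%, below the literal 5% ceiling in SAP 8.4. Study success rests on noninferiority alone: "The study is considered successful if primary objective 1a is achieved". Objectives 2a and 2b keep their own 98.73% intervals.

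Much of this stands as a limit on weight. The bad case is possible rather than expected, and no inflation of the 2a or 2b tests themselves has been shown. It does not rescue the justification. Type I error is the maximum over the stated null, and the protocol's level is one-sided 0.025, which is exceeded at every correlation examined up to 0.9. One dominant strain is also conceivable: the planned differences run from 0.07 to 0.26 and come from a trivalent study.

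On cost, A/H1N1 at 90% power is the stated basis for the sample size. Restoring it at the tighter level would need about 2,334 evaluable subjects: 4 × (0.46/0.07)² × (2.394 + 1.282)². That matters only if strain-level power for A/H1N1 is a goal in itself; 1b requires any two strains.

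**Conclusion.** The concern holds. The 0.014 is correct arithmetic for a narrower null than the one written. Over the stated null, the one-sided error of 1b reaches 7.3% under independence and cannot exceed 7.5%. At assumed common correlations of 0.3 to 0.9 it is 6.8% to 4.2%, against 2.5% intended. The two-sided 5% FWER stated in SAP 11.4 is therefore not delivered for 1b.

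The noninferiority conclusion and the study-success statement are untouched. With no superior strain and independence, the rule is very conservative (0.36%). This should be fixed, but it does not threaten the trial's main conclusion.

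**What to change.** For 1b only, require the upper limit of the two-sided 98.33% CI to be below 1.0 for at least 2 of 4 strains. Leave the 95% intervals for 1a as they are. Make the change in the protocol synopsis, 2.1.1, 8.2.1.3, 8.4.2.3.1, 8.4.2.3.3 and 8.5, and in SAP 2.1, 5, 8.4, 11.2 and 11.4. Delete the 0.014 argument and restate A/H1N1 strain-level superiority power as 80%.

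If 95% intervals are kept, restate the 1b null as all four strains null, limit the claim to superiority in at least one strain, and drop the statement that FWER is controlled for at least two. This rewrites a primary objective. The global-null error also depends on correlation: 0.36% under independence, but 2.7% at an assumed 0.9.

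Editorial: in SAP 8.4, replace the alpha⁴ figure for four-of-four success with the statement that all eight 1a intervals must pass, so the worst-case one-sided error is 2.5%. The conclusion that 1a needs no adjustment stands.

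Cost: an amendment to a primary success criterion, with sponsor, IRB/EC and, where required, health authority approval (Protocol 13.4), credible only before unblinding. No extra subjects are needed for 1b on the planning values. The price is A/H1N1 power of 80% instead of 90%, and 1b power of 80.5% instead of 90.5% if only A/H3N2 and A/H1N1 are superior. If the criterion can no longer be changed, the 0.014 argument and the FWER statement should still be corrected and the worst-case error reported.

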8.5 Subgroups

Adjusted (same model as the main analysis by subgroup with subgroup factor removed if it is in the main model) and unadjusted immunogenicity analysis of the GMTs and SCRs will be performed by stratifying for the following subgroups:

- Age cohort (50-59 and 60-64 years of age)
- Previous vaccination history (Yes and No)
- Sex
- Race
- Ethnicity
- Comorbidity risk score (<50 and ≥ 50)

Safety analysis will be performed by stratifying for the following subgroups:

- Age cohort (50-59 and 60-64 years of age)
- Previous vaccination history (Yes and No)
- Sex
- Race
- Ethnicity
- Comorbidity risk score (<50 and ≥ 50)

8.6 Data Transformation

Distributions of antibodies are generally skewed to the right and approximately log-normally distributed. Therefore, prior to any statistical analysis that assumes normally distributed observations, antibody titers will be \log_{10} -transformed. GMTs and their 95% CIs will be then computed by exponentiating (base 10) the means and 95% CIs of the \log_{10} transformed titers.

8.7 Derived and Computed Variables

Demographics

Body Mass Index (kg/m^2) will be calculated using the following formula:

$$\text{Body weight (kg) / Height}^2 (\text{m}^2).$$

Immunogenicity

Values below the lower limit of quantification (LLOQ) will be set to half that limit. Values above the upper limit of quantification (ULOQ) will be set to the value of this upper limit.

Seroconversion based on HI (or microneutralization [MN]) antibodies titer is defined as binary variable for subjects with non-missing values pre-vaccination- and post-vaccination as:

= 1, if seroconverted (defined as a \geq 4-fold increase in titer post-vaccination in those with pre-vaccination titer above or equal the LLOQ (1:10), or a post-vaccination titer \geq 1:40 for subjects with pre-vaccination titer below the LLOQ (1:10))

= 0, otherwise

Fold increase is defined as the post-vaccination titer divided by the pre-vaccination titer.

Geometric Mean Titer

The GMT will be calculated using the following formula:

$$10^{\left\{ \frac{\sum_{i=1}^n \log_{10}(t_i)}{n} \right\}}$$

where t_1, t_2, \dots, t_n are n observed immunogenicity titers. The 95% CIs for GMT will be calculated as $10^{\{M-t_{0.975,n-1}SE\}}$, $10^{\{M+t_{0.975,n-1}SE\}}$; where M and SE are the means and standard error of \log_{10} - transformed titers, respectively.

Comorbidity Score (Hak score)

For each subject, the Comorbidity Score (Hak score) is derived through the summation of the scores of the applicable characteristics. Missing values will not be replaced.

Characteristic	Score ^a
Age, years	
<70	0
70-74	14
75-79	28
80-89	42
≥90	56
Sex	
Female	0
Male	9
Outpatient visits during the previous year	
0	0
1-6	11
7-12	22
>13	33
Previous hospitalization due to pneumonia or influenza	
No	0
Yes	63
Comorbidity^b	
Pulmonary disease	18
Heart disease	6
Renal disease or renal transplant	12
Dementia or stroke	22
Non-hematological and hematological cancer	48
Subject total score	
Notes:	
a.	The prognostic score for a given subject can be obtained by adding the scores for each applicable characteristic.
b.	Pre-existing medical conditions of eligible subjects will be scored following a judgment by the investigator.

Solicited Adverse Events

For details see [section 13.2](#).

Unsolicited Adverse Events

All AEs will be characterized according to the date of occurrence related to the vaccination as follows:

- **Pre-vaccination:** start date before the date of injection of study vaccine or indicated as on injection day but before injection are collected as medical history.
- **Emergence during vaccination phase:** all other cases.

Note: If an AE start date is missing or unknown and no indication is provided on the timing, the AE will be considered as emergent.

When start and/or end dates of an AE are only partially known, AEs will be categorized as emergent before, during, or after vaccination phase using the following rules:

- If the partial end date is before ($<$) the vaccination (i.e., year or year & month is/are before the study vaccination year or year & month) then the AE is pre-vaccination.
- If the partial start date is equal or after (\geq) the study vaccination (i.e., year or year & month is/are after or the same as the study injection year or year & month) then the AE is emergent during vaccination phase.

All AEs emergent during vaccination phase will be categorized as occurring during the period of 21 days following the study vaccination based on the start date, i.e. Day 1 to Day 22 included. If start date is missing or incomplete, events will be counted as yes during the period of 21 days following the date of study vaccination.

Adverse events that meet none of the following criteria SAE, AESI, or AE leading to withdrawal, and had a start date more than 21 days after the last vaccination are not to be recorded. However, if recorded, these AEs should be flagged (i.e. exclusion flag), excluded from analysis and listed separately. The same will be done with AEs starting before study vaccination injection.

The **maximum event severity** is the greatest severity associated with a preferred term (PT) for a reported AE according to the following order: Mild < Moderate < Severe.

Multiple AEs with the same PT for the same subject are counted only once with the maximum event severity.

Vaccination-related Adverse Events are those for which the cause has been evaluated by the investigator, and recorded as possibly related, probably related or missing.

Prior and Concomitant Medications and Vaccines

All medications and vaccines will be characterized according to the start and end date of occurrence related to the vaccination as follows:

- **Prior Medication and Vaccines:** start date before the date of injection of study vaccine.
- **Concomitant medications and vaccinations:** any medication and vaccination on or after the date of injection study vaccination.

Concomitant medication with partial date is treated in a similar way as treatment emergent AE with missing date. Concomitant medication and vaccines with start date after End of Study (EOS) date will be excluded from analysis. Concomitant medication that results from adverse events that meet none of the following criteria SAE, AESI, or AE leading to withdrawal, and had a start date more than 21 days after the study vaccination will be flagged (i.e. exclusion flag), and excluded from analysis.

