7.1.2 Unsolicited Adverse Events

An unsolicited AE is an AE that was not solicited using a Subject eDiary and that was spontaneously communicated by a subject who was vaccinated.

Potential unsolicited AEs may be medically attended (defined as symptoms or illnesses requiring hospitalization, or emergency room visit, or visit to/by a qualified healthcare professional) or were of concern to the subject. In case of such events, subjects will be instructed to contact the site as soon as possible. The detailed information about the reported unsolicited AEs will be collected by the qualified site personnel during the interview and will be documented in the subject's records. In this study, all unsolicited AEs will be collected during the treatment period (Day 1-Day 22), and only specific unsolicited AEs (SAEs, AEs leading to withdrawal and AESIs) will be collected during the follow-up period (Day 23-Day 271). In addition, any unsolicited AEs reported within 30 minutes after the study vaccination will be collected as immediate postvaccination AEs.

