8.1.2.1 Secondary Safety Endpoint(s)

Safety and reactogenicity will be assessed by the frequency and severity of:

- Solicited local and systemic AEs for 7 days following vaccination (Day 1 through Day 7);
- All unsolicited AEs for 21 days following vaccination (Day 1 through Day 22);
- SAEs, AEs leading to withdrawal from the study, AESIs as collected from Day 1 through Day 271.

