13.3 Unsolicited Adverse Events

This analysis applies to all unsolicited AEs occurring during the study, judged either as probably related, possibly related, or not related to vaccination by the investigator, recorded in the AE eCRF, with a start date on (but with onset after vaccination) or after the date of vaccination.

The original verbatim terms used by investigators to identify AEs in the eCRFs will be mapped to PTs using the MedDRA dictionary.

The AEs will then be grouped by MedDRA PTs into frequency tables according to SOC. All reported AEs, as well as AEs judged by the investigator as at least possibly related to study vaccine, will be summarized according to SOC and the PT within SOC. These summaries will be presented by the vaccine group and by interval of study observation (Day 1-Day 22, Day 23-EOS, Day 1-EOS). When an AE occurs more than once for a subject, the maximal severity and strongest relationship to the vaccine will be counted.

The assignment to time intervals will be done by day of onset.

The AE summaries will be presented by SOC and PT and different periods of onset depending on the category of events.

- Unsolicited AEs during the 30 minutes post vaccination
- SAEs
- Unsolicited AEs that are possibly or probably related to vaccine
- AESIs
- AEs leading to withdrawal
- Deaths

All tables will be produced by treatment.

An overview summary of AEs, including frequencies and percentages of any AEs (by mild/moderate/severe grade), related AEs, AEs leading to withdrawal, any SAEs, related SAEs, AESIs and deaths will also be presented.

In addition, summary of subjects with unsolicited non-serious adverse event reported by >5% of subjects and summary of subjects with unsolicited non-serious or solicited adverse event reported

by >5% of subjects in any vaccine group sorted by SOC and PT will be provided for clinicaltrials.gov and EudraCT.eu posting purposes.

Separate data listings of all AEs, SAEs, AESIs, AE leading to withdrawal and AE leading to death will be provided by study treatment, subject and onset date.

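### SAP 8.7 counts every emergent AE with an incomplete start date in Day 1-22, even when its recorded month lies wholly after Day 22, so late SAEs, AESIs and AEs leading to withdrawal can be shown in the wrong interval

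*SAP*

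**What the plan says.** SAP 8.7 (Unsolicited Adverse Events) handles partial dates in two steps. First, it uses the known part of the date to separate pre-vaccination from emergent events. An event is emergent if its "year or year & month is/are after or the same as the study injection year or year & month", and there is no upper limit. Second, it places emergent events in the 21-day window, and for those without a full date it says: "If start date is missing or incomplete, events will be counted as yes during the period of 21 days".

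A further paragraph of SAP 8.7 deals with events that start more than 21 days after vaccination and are not SAEs, AESIs or AEs leading to withdrawal: "if recorded, these AEs should be flagged (i.e. exclusion flag), excluded from analysis and listed separately".

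SAP 13.3 says of the all-AE and related-AE tables: "These summaries will be presented by the vaccine group and by interval of study observation (Day 1-Day 22, Day 23-EOS, Day 1-EOS". It adds: "The assignment to time intervals will be done by day of onset". For the further summaries by AE category it allows "different periods of onset depending on the category of events".

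Protocol 7.1.2 limits late collection: "only specific unsolicited AEs (SAEs, AEs leading to withdrawal and AESIs) will be collected during the follow-up period (Day 23-Day 271". The corresponding endpoint in Protocol 8.1.2.1 covers the whole study: "SAEs, AEs leading to withdrawal from the study, AESIs as collected from Day 1 through Day 271".

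**The concern.** The SAP uses the recorded year and month to decide whether an event came before or after vaccination. It then ignores the same information when deciding whether the event came before or after Day 22. Defaulting to the early window is a normal cautious choice when onset could have been in that window. Here it also applies when the recorded month rules that window out.

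The consequence falls on the events of most interest late in follow-up. After Day 22 only SAEs, AESIs and AEs leading to withdrawal are collected, and any other late event is to be flagged out. The Day 23-EOS part of the all-AE and related-AE summaries therefore holds only the event types that this rule can move. Each event moved adds one to Day 1-22 and takes one from Day 23-EOS. These events may be few, so a single misplaced one could visibly change a cell, and time since vaccination is exactly what the split is meant to show.

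**Working it through.** The plan gives no figure to reproduce, because this is a classification rule. The check follows the rule through one case and then counts calendar days.

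**Is there another rule that would apply?**
- SAP 13.3 assigns by day of onset. An incomplete date has no onset day, and 13.3 does not say what to do then.
- Protocol 8.4.3.1.3 says that missing unsolicited AEs are not imputed. It gives no rule for partial dates.
- The exclusion flag in SAP 8.7 does not cover SAEs, AESIs or AEs leading to withdrawal. For other late AEs it can reasonably be read as governing, so no conflict between rules is claimed there.
- The lead-in to the partial-date rules in SAP 8.7 mentions a class of events after the vaccination phase, but no rule assigns anything to it. Later months go to the emergent class.

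The sentence in SAP 8.7 is therefore the only instruction available.

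**Worked case (vaccination on 15 Dec 2021 is assumed; Day 1 = vaccination).** Date of Day d = vaccination date + (d − 1) days.
- Day 22 = 15 Dec 2021 + 21 days = 5 Jan 2022.
- Day 271 = 15 Dec 2021 + 270 days = 11 Sep 2022.
- 1 Feb 2022 = Day 49. A month-only date from February 2022 onward cannot lie in Day 1-22.
- Late days in such months: 271 − 49 + 1 = 223 of 271 − 23 + 1 = 249, or 223/249 = 89.6%.
- An SAE dated June 2022 with the day unknown began between Day 169 (1 Jun) and Day 198 (30 Jun). Under SAP 8.7 it is emergent, its date is incomplete, and it is counted in Day 1-22.

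**All vaccination dates in a year.** For each of 365 assumed vaccination dates, 1 Aug 2021 to 31 Jul 2022, the days in Day 23-271 that lie in a calendar month containing no Day 1-22 date were counted.

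| | Days of 249 | Share |
|---|---|---|
| Minimum (e.g. vaccination on 11 Dec 2021) | 219 | 88.0% |
| Mean | 234.3 | 94.1% |
| Maximum (e.g. vaccination on 10 Dec 2021) | 249 | 100% |

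The two extremes can be checked by hand. For 11 Dec, Day 22 is 1 Jan 2022, so 2 to 31 Jan (30 days) remain ambiguous and 249 − 30 = 219. For 10 Dec, Day 22 is 31 Dec 2021, so every late day lies in a later month.

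If only the year is known, the share that can be settled runs from 0% to 100%, depending on the vaccination date (365 assumed dates, 1 Sep 2021 to 31 Aug 2022).

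**The case against.** The strongest objection concerns scope and weight.

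- **Inference.** SAP 8.7 says that such events count in the 21-day period. It does not say in words that they leave Day 23-EOS. This is true, but an event assigned to one interval by onset cannot also be assigned to the next, and no other rule would put it there.
- **Which tables.** Because onset periods may differ by AE category, the SAP does not say that the separate SAE, AESI and withdrawal tables are split at Day 22, and the table shells are not in the SAP text. This stands. The point is limited to summaries that are split at Day 22, which SAP 13.3 requires for all AEs and for related AEs.
- **Frequency.** The percentages are shares of calendar days, given a late event with a known month and an unknown day. SAEs and AESIs are reported within 24 hours (Protocol 7.1.4.1 and 7.1.5), entries are checked against source (9.2) and queries are raised (10.2), so such dates should be uncommon. This stands.
- **Consequence.** The safety analysis is descriptive and tests no hypothesis (Protocol 8.4.3.1.4 and 8.4.3.1.6), the rule is the same in both arms, and listings by onset date let a reader see the recorded date. This stands too. Calling the rule conservative answers only half the point: it can overstate early events, but it also understates late ones.

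**Conclusion.** The rule is wrong as written for one class of event: an SAE, AESI or AE leading to withdrawal whose incomplete start date nevertheless shows onset after Day 22. Following the SAP puts it in an interval that its own recorded month excludes. For month-only dates the recorded month settles the interval for 88% to 100% of late onset days (mean 94%), so the information discarded is nearly always decisive.

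These shares rest on the assumed vaccination dates and on equal weight for each day of Day 23-271. They are not event rates. The effect is confined to a descriptive interval split. Totals over Day 1-EOS, the Day 1-271 endpoint, listings and immunogenicity do not change. It should be corrected because the correction is simple and the affected column contains only serious or specially monitored events.

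**What to change.** Replace the SAP 8.7 sentence on missing or incomplete start dates with:

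> For an AE emergent after vaccination with an incomplete start date, if the known year/month lies wholly after Day 22, an SAE, AESI or AE leading to withdrawal is assigned to Day 23-EOS, and any other AE is given the exclusion flag. If the known part is compatible with Day 1-22, or the start date is wholly missing, the AE is assigned to Day 1-22.

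This keeps the cautious default wherever onset could have been in Day 1-22, and it applies the SAP's existing exclusion flag to other late events. The pre-vaccination rules stay as they are. The concomitant-medication rule also stays as written. Because it handles partial dates by analogy with AEs, a short note that this change does not carry over to it would avoid doubt.

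The cost is one sentence in the SAP and a small programming change. No new data are needed.
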